METHODS AND ANALYSIS: This is a 1,232 patient, block-randomized, double-blinded, comparative effectiveness trial. Patients older than sixty, undergoing volatile agent-based general anesthesia for major surgery, are eligible. Subjects are randomized to one of two anesthetic approaches. One group receives general anesthesia with clinicians blinded to EEG monitoring. The other group receives EEG-guidance of anesthetic agent administration. The outcomes of postoperative delirium (≤ 5 days), falls (≤ 1 month) and health-

between groups will be presented with 95% confidence intervals, and will be considered statistically significant at a two-sided $p<0.05$.

ETHICS AND DISSEMINATION: ENGAGES is approved by the ethics board at Washington University.

Recruitment began in January 2015. Dissemination plans include presentations at scientific conferences, scientific publications, internet-based educational materials, and mass media.

REGISTRATION DETAILS: ENGAGES is registered on clinicaltrials.gov, NCT02241655 (updated February 2015).

Strengths

- The ENGAGES study is a pragmatic clinical trial, conducted in a real world clinical setting.
- The study will enroll older patients, who are under-studied in clinical research.
- The primary outcome, postoperative delirium, is important to patients, healthcare providers and society.
- The electroencephalography-guided anesthetic protocol is straightforward and inexpensive; it would be feasible to disseminate and implement broadly.
- The study utilizes reliable and granular data from the perioperative electronic medical record and incorporates data from a large registry of postoperative patient reported outcomes.

Limitations

- A single clinical trial should seldom be regarded as definitive; if the results of this trial do suggest that EEG-guidance of anesthesia decreases postoperative delirium, it will be necessary to replicate this finding in future studies.
- While patients and those assessing the primary outcome are blinded, the inability to blind clinicians to the trial allocation group is a potential source of bias and confounding.
- The effectiveness of the electroencephalography-guided anesthetic protocol will depend on clinicians' adherence to the protocol.
- As delirium is a fluctuating disorder, it may occasionally be missed despite rigorous and validated assessment methods.

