Randomization will be performed at the patient level using computer-generated assignment. Eligible patients who provided written informed consent will be randomized to receive the intraoperative electroencephalography-guided protocol or routine care. In order to ensure that there is not major imbalance between group assignments with respect to history of falls and cardiac surgery, subjects will be randomized (1:1) between the EEG-guided and routine care groups in blocks of 20 within these four strata (i.e., cardiac surgery with a history of falls within 6 months, cardiac surgery without a history of falls within 6 months, non-cardiac surgery with a history of falls within 6 months; and non-cardiac surgery without a history of falls within 6 months). Trained members of the research team will enroll participants and will implement the assignment of participants to the EEG-guided or usual care protocols. Group assignment will be revealed to members of the anesthetic team only when the patient enters the operating room by opening a sequentially numbered, opaque, sealed envelope in a sequence generated by one of the study's data analysts. Patients and their families will be blinded to group allocation and different members of the research team will assist with the intervention in the operating room (will not be blinded to the intervention) from those conducting the postoperative assessments (will be blinded to the intervention).^{51,52} To reduce predictability of a random sequence, details of patients already randomized and prior group assignments will be recorded in a separate document that is unavailable to those who enroll participants and assign interventions.

Primary Intervention – EEG-guided Anesthetic Protocol

The primary intervention to which patients will be randomized in this study is a pragmatic EEG-guided anesthetic protocol (See Appendix). All anesthesia practitioners will receive a targeted educational session on recognition of EEG patterns typically occurring during general anesthesia. The content will be similar to that described in an article where we demonstrated that anesthesiologists could estimate BIS (processed EEG

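### A single published block size of 20, with no stated separation of enrolling staff from staff who see assignments, leaves up to about 9% of allocations foreseeable in the worst case; varied block sizes would be a cheap improvement

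*Combined protocol and SAP*

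**What the plan says.** The relevant text is in the Combined protocol and SAP, Randomization and Blinding.

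- **Scheme.** "subjects will be randomized (1:1) between the EEG-guided and routine care groups in blocks of 20 within these four strata". The strata are cardiac or non-cardiac surgery, with or without a fall in the previous six months. One size is given and no variation is mentioned.
- **Roles.** "Trained members of the research team will enroll participants and will implement the assignment of participants to the EEG-guided or usual care protocols".
- **Concealment.** "Group assignment will be revealed to members of the anesthetic team only when the patient enters the operating room", and this is done "by opening a sequentially numbered, opaque, sealed envelope in a sequence generated by one of the study's data analysts".
- **Protection against prediction.** To make the sequence harder to guess, details of "prior group assignments will be recorded in a separate document that is unavailable to those who enroll participants and assign interventions".
- **Separation of staff.** Research staff who help in the operating room know the arm. They are described as different people from the postoperative assessors. Nothing says that they are different from the people who enroll.

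The Research Design Overview describes one hospital and 1,232 patients. The Limitations list after the abstract accepts that "the inability to blind clinicians to the trial allocation group is a potential source of bias and confounding".

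**The concern.** With a fixed and known block of 10 + 10, the rest of the block is determined as soon as one arm has been used ten times. The protocol recognizes the general problem, since it keeps the log of earlier assignments from those who enroll and assign. But whoever implements an assignment, or assists in the operating room, learns the arm directly. Withholding the written log does not stop such a person from keeping a tally. If that person also enrolls patients, which the text does not rule out, concealment at the end of a block depends on their not counting.

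What would be at stake is selection. Someone who foresees the next assignment might influence whether or when a consented patient goes forward, and so disturb the prognostic balance between arms. The primary delirium comparison is an unadjusted chi-square test (Statistical Analyses, part i), so it would not correct for such an imbalance.

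**Working it through.** The documents state no predictability figure, so there is none to reproduce.

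**Inputs.** From Randomization and Blinding: 1:1 allocation and block size 20, so m = 10 per arm. From the Research Design Overview: N = 1,232, which is 1,232/20 = 61.6 blocks.

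**1. Worst case: block size known and every earlier assignment in the block seen.**

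- Expected assignments left once one arm is used up: 2m/(m + 1) = 20/11 = 1.818 per block.
- Share: 1.818/20 = 9.09%, and 0.0909 × 1,232 = 112. Allowing for incomplete last blocks in four strata, simulation gives about 109 (8.8%).
- Assignments predictable with probability 75% or more: after i and j assignments to the two arms, the state has probability C(i+j, i) × C(20−i−j, 10−i)/C(20, 10). The best guess is right with probability max(10−i, 10−j)/(20−i−j). Adding up the states where this is at least 0.75 gives 3.06 per block, or 15.3% (about 188 of 1,232).
- Average best-guess accuracy: [m + 2^(2m−1)/C(2m, m) − 1/2]/(2m) = [10 + 524,288/184,756 − 0.5]/20 = 12.34/20 = 61.7%, against 50% by chance.

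**2. Partial observation.** Let q be the chance that the guesser sees each earlier assignment in the block. The documents give no value, so these are assumptions. The results are simulated and take the block boundaries as known.

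| q | Known with certainty | Of 1,232 |
|---|---|---|
| 1.00 | 9.1% | 112 |
| 0.95 | 5.5% | about 68 |
| 0.90 | 3.2% | about 39 |
| 0.75 | 0.5% | about 6 |
| 0.50 | 0.01% | fewer than 1 |

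Near-certainty fades more slowly: 9.6% of assignments remain predictable at 75% or more with q = 0.90, and 4.6% with q = 0.75.

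**3. Is 20 short?** No. By the same formula the worst-case certain share, 1/(m + 1), is 33% for blocks of 4, 25% for 6, 20% for 8 and 17% for 10.

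**4. What varying the size would gain.** Suppose sizes are drawn at random from 12, 16, 20, 24 and 28, the guesser knows that set, and all earlier assignments are seen. Repeated simulations give 0.3% to 0.5% certain (about 4 to 6 of 1,232), 6% to 7% predictable at 75% or more, and an average accuracy of 61.4% to 61.6%. Average guessing hardly changes. The gain lies in removing the certain and near-certain assignments.

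**The case against.** The strongest reply is that the worst case is remote.

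- It needs one person who knows the block size and misses nothing in a stratum. Missing a quarter of the assignments brings the certain share to 0.5%.
- Consent comes before the envelope is opened. If envelopes are used in order of surgery, which the text does not say, an enroller would also have to foresee that order within the stratum.
- Many practitioners give the anesthetics, so a complete tally by any one of them is unlikely.
- Nothing in the documents suggests that research staff can delay elective surgery or choose the practitioner.
- The one-year SAP plans adjusted models for mortality, quality of life and falls. These partly address imbalance in measured factors for those outcomes, though not for delirium.

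All of this stands, and it is why the point is minor. It does not close the gap, because no sentence keeps enrollers away from assignments or keeps the block size from them.

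A reader might also infer three stronger things that the documents do not support:

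- **That the same individuals enroll patients and watch each envelope being opened.** The text gives both duties to a team. It names the anesthetic team as those to whom the arm is revealed, and does not say that enrollers are present.
- **That the withheld log is the only protection.** The numbered opaque envelopes, the analyst-generated sequence and the late reveal are protections too.
- **That about 9% of assignments were in fact foreseeable.** That figure is a ceiling under full knowledge, not a property of the trial as run.

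**Conclusion.** The point holds as a low-severity design improvement. The protocol prints one fixed block size per stratum and leaves unstated whether those who enroll are separate from those who open or see assignments. The 9% and 15% figures rest on a known block size and complete observation within the block. The lower figures rest on assumed observation rates. The documents show neither that anyone predicted assignments nor that the arms were biased. That clinicians know the arm during surgery is a separate matter, which the protocol already discloses.

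**What to change.** For any block not yet started:

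1. Replace the single block size in Randomization and Blinding with randomly permuted blocks of randomly varying size, within the same four strata.
2. Keep the sizes in a restricted document held by the analyst who generates the list, and out of the protocol.
3. State that staff who enroll patients do not open or see assignments, where existing staffing allows.

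The cost is regenerating the unused part of the list and its envelopes, and revising a sentence or two. No extra patients or procedures are needed. The drawback is a slightly larger possible imbalance in an incomplete final block: with sizes up to 28, at most 14 per stratum instead of 10, which is small beside 616 per arm.

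The change may come too late. The protocol lists recruitment as open, but the one-year SAP gives surgery dates of January 2015 to May 2018 and analyzes 1,232 randomized patients. If allocation is complete, the remaining step is to report as a limitation that the block size was fixed, who knew it, and who saw assignments.

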assessments must view and rate nine videos of standard interviews of actors depicting delirious and non-delirious patients. This process will help to demonstrate the success of the training process and the extent to which researchers reproducibly score the CAM. To establish the reliability of delirium assessments in the clinical setting, trained members of the research team will separately assess 30 patients not enrolled in the ENGAGES study at similar time points (e.g., within two hours of each other). These assessments will determine the test-retest reliability of delirium assessments by the research team. This approach will provide > 90% power to demonstrate a Kappa statistic of >0.6, representing substantial or greater agreement between raters.⁹⁶

A structured process will be implemented to assess and ensure the quality of the delirium assessments. Every delirium assessment will be reviewed within three days with a fellow member of the research team to assess internal consistency of scoring and completeness. On a weekly basis, investigators at Washington University will review all the delirium assessments, will address methodological inconsistencies, and will attempt to resolve controversies. Monthly, there will be a teleconference including investigators from Hebrew SeniorLife/Harvard University and from Washington University to review challenging delirium assessments and to ensure that the rigor of assessments remains appropriate. During these conferences, the need for focused and comprehensive refresher training in delirium assessment⁹⁵ will be determined.

If participants agree, these assessments may be videotaped for training and education of the research team. The videotapes will include the patients face.

ii) Health-related Quality of Life (Aims 2 and 3 in Figure 2)

As part of the ongoing SATISFY-SOS study, patient self-reported Health-related Quality of Life information will be assessed through the Veteran's RAND 12-item Health Survey at baseline (preoperatively) and during follow-up (30-day and 1-year). The VR-12 was derived from the Veterans RAND 36 Item Health Survey (VR-36) and contains 12 items relating to quality of life, including physical and mental health, as well as specific questions about functional status. Physical and Mental Health Summary Scores will be calculated. The VR-12 has been validated and is widely applied as a metric for tracking health-related quality of life in the United States.⁹⁷

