We will design a prospective matched cohort study using the ENGAGES participants (received multi-

All statistical analyses will be performed using SAS, version 9.4 (SAS Institute, Inc., Cary, North Carolina). All tests will be two-sided and by arbitrary convention¹⁰⁵ will be considered statistically significant at a $p<0.05$, and all results will be presented with estimates and 95% confidence intervals. However, based on the uncertain prior probability (plausibility) of the alternative hypothesis¹⁰⁶ (i.e., EEG guidance of anesthesia decreases postoperative delirium) and concerns raised about lack of reproducibility in science^{107,108}, a statistically significant result with a p value just <0.05 should be considered as preliminary, and future studies should be conducted for corroboration. A more stringent p value (e.g., $p<0.005$) would be required to conclude that subsequent studies would be very likely to reproduce these results with a p value <0.05 .¹⁰⁹ Apart from statistical significance, the ultimate decision regarding the routine implementation of EEG-guidance of general anesthesia in preventing postoperative delirium will also depend on the estimated effect size of this intervention.

Sample Size Calculations

All sample size calculations have been performed using SAS PROC POWER.

i) Decrease in Delirium

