Our sample size calculations are based on the anticipated delirium incidence and effect size for our primary endpoint analysis. Based on results of a previously published meta-analysis of four studies investigating the use of BIS-guided anesthetic administration, we conservatively assume an incidence of postoperative delirium in the routine anesthesia care group of 25%.²⁹ We performed a sample size sensitivity analysis and calculated different scenarios with different values for the delirium incidence in the intervention arm and corresponding power (80%, 90%, and 95%). With a two sided alpha $<5\%$ and 1,232 patients (616 per arm), the trial will have $>95\%$ power to detect an absolute decrease in delirium incidence $\geq 9\%$, $>90\%$ power to detect a decrease in delirium incidence $\geq 8\%$, and $>80\%$ power to detect a decrease in delirium incidence $\geq 7\%$. With a 7% decrease in delirium incidence, the 95% confidence interval would be approximately 3% to 12%. Even a 3% decrease in delirium incidence would be clinically important, suggesting that delirium would be prevented in one out of every 33 at risk patients who received EEG-guidance of general anesthesia.

ii) Health Related Quality of Life

The overall sample size of our study is defined through estimations of the primary outcome (delirium). For secondary analyses, we assume that ~80% of our trial population (~1,000 participants) will have completed the trial and the 1-year follow-up survey. With this sample size of 1,000, we can detect a difference of 0.5 points (standard deviation of 2.5) in the mean change of Physical Health Score from baseline to 1 year between the intervention and usual care group with a power of $>80\%$ and a two-sided alpha level of $p<0.05$.

iii) Postoperative Falls

This calculation is similarly based on the assumption that ~80% of our trial population (~1,000 participants) will have completed the trial and the 1-year follow-up survey. Based on a study that showed a preoperative fall prevalence of 33% over six months preoperatively in a similar patient population to the ENGAGES trial, we will conservatively assume an incidence of postoperative falls at 1-year in the routine anesthesia care group of 40%.¹¹⁰ With a sample size of 1,000, we will have $>80\%$ power to detect an absolute risk reduction of 12% between the EEG-guided and the usual care group at a two-sided alpha level of $p<0.05$.

Analysis of Pragmatic Elements of the ENGAGES Study

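### The 90% power claimed for the 30-patient rater-agreement check matches a test of kappa = 0; to show that kappa exceeds 0.6, power is far lower unless agreement is near perfect

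*Combined protocol and SAP*

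**What the plan says.** The statement is in the Combined protocol and SAP, Outcome Measures, i) Incidence of Postoperative Delirium. As part of training, "trained members of the research team will separately assess 30 patients not enrolled in the ENGAGES study at similar time points", for example within two hours of each other. The protocol then claims: "This approach will provide > 90% power to demonstrate a Kappa statistic of >0.6, representing substantial or greater agreement between raters".

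That section does not say which value of kappa is to be ruled out, what true kappa is assumed, how common delirium is expected to be among the 30 patients, at what alpha the test is made, or how many raters see each patient. Nothing elsewhere in either document fills these gaps for this check. The nearest general rule is under Statistical Analyses: "All tests will be two-sided and by arbitrary convention" judged at 0.05, with estimates and 95% confidence intervals for all results.

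**The concern.** In plain terms, to "demonstrate a Kappa statistic of >0.6" means to produce data that exclude 0.6 and below. Thirty paired yes/no ratings give a kappa with a standard error of about 0.11 to 0.13 even when the true value is as high as 0.8, so ruling out a value only 0.2 lower with more than 90% power looks implausible. Power of that order is what one expects for ruling out zero.

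The difference matters because these raters produce the CAM and CAM-ICU assessments, and a positive one is enough to classify a patient as having the primary outcome. If the sentence is taken at face value, a good-looking kappa from 30 patients could be reported as proof of substantial agreement when the data are still compatible with moderate agreement.

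**Working it through.** **Inputs from the documents.** 30 patients, claimed power above 90%, threshold 0.6 (Outcome Measures, i); two-sided 0.05 as the general convention (Statistical Analyses); 25% delirium incidence as the planning rate (Sample Size Calculations, i); 50% as the upper end of the range that the Background gives for most studies.

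**Assumptions.** Two raters per patient; prevalence *p* between 25% and 50% among the 30 patients; true kappa of 0.8, with 0.9 and 0.95 as alternatives. The documents state none of these for this check.

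**Formula.** For two raters with common prevalence *p*, the large-sample variance of kappa is V(κ)/n, with V(κ) = (1−κ)[(1−κ)(1−2κ) + κ(2−κ)/(2p(1−p))].

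**1. Reproducing the plan's figure: null 0, true kappa 0.6.**
- V(0) = 1, so the null SE is √(1/30) = 0.183 and the two-sided critical value is 1.96 × 0.183 = 0.358.
- *p* = 25%: V(0.6) = 0.4 × [−0.08 + 0.84/0.375] = 0.864, SE = 0.170, power = Φ((0.6 − 0.358)/0.170) = 92%.
- *p* = 50%: V(0.6) = 0.4 × [−0.08 + 0.84/0.5] = 0.64, SE = 0.146, power = Φ((0.6 − 0.358)/0.146) = 95%.
- Simulation gives 90%, 93% and 94% at prevalences of 25%, 35% and 50%. A goodness-of-fit calculation gives 90.8%.

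So the stated figure is reproduced, for a null of zero.

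**2. The lenient reading: the observed kappa exceeds 0.6.** By simulation this happens in 91% to 95% of samples when the true kappa is 0.8. It also happens in 49% to 50% of samples when the true kappa is exactly 0.6.

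**3. Null 0.6, true kappa 0.8 (null-variance z-test).**
- *p* = 25%: the one-sided critical value is 0.6 + 1.645 × 0.170 = 0.879. V(0.8) = 0.2 × [−0.12 + 0.96/0.375] = 0.488, SE = 0.1275, power = Φ(−0.62) = 27%. Two-sided, the critical value is 0.933 and power = Φ(−1.04) = 15%.
- *p* = 50%: the one-sided critical value is 0.6 + 1.645 × 0.146 = 0.840. V(0.8) = 0.2 × [−0.12 + 0.96/0.5] = 0.36, SE = 0.1095, power = Φ(−0.37) = 36%. Two-sided, the critical value is 0.886 and power = Φ(−0.788) = 22%.

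**4. The same question by other methods** (n = 30, two raters, true kappa 0.8, prevalence 25% to 50%):

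| Method | Power against 0.6 |
|---|---|
| Null-variance z-test, simulated, one-sided 0.05 | 28–41% |
| Null-variance z-test, simulated, two-sided 0.05 | 13–18% (as low as 10% with prevalence taken as known) |
| Goodness-of-fit, two-sided 0.05 | 22–28% |
| Goodness-of-fit, one-sided 0.05 | 33–39% |
| Critical value set by simulation under 0.6, one-sided 0.025 | 22–28% |
| Critical value set by simulation under 0.6, one-sided 0.05 | 34–41% |
| Lower limit of the 95% CI above 0.6 | 41–45% |

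The confidence-limit rule scores best partly because it is liberal at this size. A team with true kappa 0.6 passes it in about 4% to 8% of samples, against a nominal 2.5%. A one-sided 95% lower limit passes 50% to 60% of samples at true kappa 0.8, but about 10% at true kappa 0.6.

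**5. How good must agreement be?** At true kappa 0.9, the 95% CI rule passes 78% to 82% of the time and the size-controlled test 53% to 81%. At 0.95 the figures are 92% to 96% and 76% to 96%.

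**6. Precision at true kappa 0.8.** From the formula, 1.96 × 0.1095 = 0.21 to 1.96 × 0.1275 = 0.25. The simulated standard deviations are slightly larger (0.112 to 0.139), giving about ±0.22 to ±0.27.

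**7. Scale.** For 90% one-sided power against 0.6 at true kappa 0.8, n = [(1.645√V(0.6) + 1.282√V(0.8))/0.2]². At *p* = 50% this is [(1.645 × 0.8 + 1.282 × 0.6)/0.2]² = 109; at *p* = 25% it is 147. The goodness-of-fit method asks for more (138 and 180).

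**The case against.** The strongest reply is that the sentence is under-specified rather than wrong. It names no null hypothesis, and a kappa *statistic* above 0.6 can mean the observed value, in which case 91% to 95% at a true kappa of 0.8 is correct. It cites a paper on sample size for kappa, which may set out the null and alternative. The low figures need a true kappa, a number of raters and a prevalence that the protocol does not give; with three to five raters per patient, size-controlled power against 0.6 at true kappa 0.8 is 37% to 77%. All of this stands as far as it goes. It does not rescue the sentence. A check that a team with kappa of exactly 0.6 passes half the time does not demonstrate more than 0.6. None of the variants tried reaches 90% at a true kappa of 0.8, even with five raters. And whatever the cited paper assumes is not carried into the protocol.

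A reader might infer that 30 patients give 90% power against kappa = 0 and nothing else. That is too strong: about 90% is also reached against 0.2 when the true kappa is 0.8, and against 0.6 when agreement is near perfect, or at a true kappa of 0.9 with several raters.

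A reader might also infer that the primary endpoint is unreliable. The documents do not support that. A positive chart review, done blind to the CAM result, is diagnostic in its own right. Raters must also score nine training videos, every assessment is reviewed within three days, and there are weekly and monthly reviews with retraining where needed. No pass/fail rule is attached to the 30-patient exercise.

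**Conclusion.** The concern holds as a minor point of wording and reporting. The claimed power above 90% is reproduced for rejecting kappa = 0 when the true kappa is 0.6, which is evidence of better-than-chance agreement and not of substantial agreement. For showing that kappa exceeds 0.6, and assuming a true kappa of 0.8, two raters and 25% to 50% prevalence, power is roughly 20% to 45% depending on method, sidedness and prevalence. It can be as low as 10% with the strictest test and is higher only with more raters or rules that inflate the false-pass rate. It approaches 90% only near a true kappa of 0.95, and not by every method even there. The true kappa and the number of raters are assumptions; the direction of the conclusion does not depend on their exact values short of near-perfect agreement. The exercise uses patients outside the trial, so neither the between-arm comparison of delirium nor the sample size of 1,232 is affected.

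**What to change.** Replace the power sentence with one that says what the exercise can show, for example: *With 30 patients, each assessed by two raters, there is about 90% power to reject kappa = 0 if the true kappa is 0.6; at a true kappa of 0.8 the 95% confidence interval will be about ±0.22 to ±0.27.* State the prevalence, alpha and number of raters assumed. Report kappa with its 95% confidence interval, as Statistical Analyses already promises for all results. Claim substantial agreement only if the lower limit exceeds 0.6; otherwise give the estimate and interval without that label. Add that the usual large-sample interval is somewhat liberal at 30 patients (about 4% to 8% false passes at a true kappa of 0.6, against a nominal 2.5%).

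The cost is a few lines of protocol text and a less favourable claim about reliability. No extra patients are needed.

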We will follow the intention-to-treat principle for all analyses. The primary endpoint of our analysis is the incidence of postoperative delirium as defined previously. The incidence of delirium will be compared between groups using a chi-square test, and the difference in delirium incidence with 95% confidence intervals will be calculated. Prespecified exploratory subgroup analyses: we will test for effect modification by known baseline delirium risk factors (i.e., age [<70 and ≥ 70], sex, history of falls, and type of surgery [cardiac versus non-cardiac]).

ii) Effectiveness of EEG-guided anesthesia protocol in improving patient reported outcomes of health-related quality of life and preventing postoperative falls (Aim 2 in Figure 2)

Health-related quality of life

Random effects regression models based on PROC MIXED in SAS will be used to compare Physical Summary Score change over 12 months between the intervention and usual care group by introducing terms for time, indicator variables for treatment group and time x treatment group interactions with the latter set of regression coefficients of primary interest. The model will be controlled for baseline health-related quality of life. Potential confounding factors including age, gender and relevant comorbidities will be evaluated and controlled for in the model. We will utilize the same analysis approach to evaluate the Mental Summary Scores.

The analysis is primarily based on the following model: $Y_{it} = \alpha + \beta_1 t + \beta_{2A} X_{i1} + \beta_{3A} X_{i1}t + \beta_4 Y_{i0} + e_{it}$ (1) where Y_{it} = QOL for subject i at time t , where $t = 0$ for baseline, $t = 1$ for 12 months. $X_{i1} = 1$ if i th subject is in the Intervention group, = 0 otherwise $e_{it} \sim N(0, \sigma^2)$ β_{3A} is the mean difference in Physical Summary Score change between the Intervention and usual care groups. The coefficient β_{2A} allows for mean differences in Physical Summary Scores between groups at baseline. The coefficient β_4 allows the change in Physical Summary Score to depend on initial level.

Postoperative falls

Chi square test will be used to compare the incidence of falls at 12-months postoperatively between patients in the EEG-guided and in the usual care groups.

iii) Explore whether a multi-component safety intervention is associated with improved patient reported health-related quality of life and decreased incidence of postoperative falls (Aim 3 in Figure 2)

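### The primary delirium test and risk difference ignore the four randomisation strata; if the strata are prognostic, the test is slightly conservative and the interval slightly too wide (minor, efficiency and calibration only)

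*Combined protocol and SAP*

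**What the plan says.** The protocol's section Randomization and Blinding gives the purpose of stratifying, "In order to ensure that there is not major imbalance between group assignments with respect to history of falls and cardiac surgery", and the method: "subjects will be randomized (1:1) between the EEG-guided and routine care groups in blocks of 20 within these four strata". The strata cross cardiac with non-cardiac surgery and a fall in the previous six months with none.

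Statistical Analyses i) sets the primary test: "The incidence of delirium will be compared between groups using a chi-square test". For the effect estimate, the same sentence of the plan adds that "the difference in delirium incidence with 95% confidence intervals will be calculated". It states no stratification or covariate adjustment. The two factors return only in exploratory subgroup analyses: "we will test for effect modification by known baseline delirium risk factors", a list that includes falls history and type of surgery.

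The separate SAP covers one-year outcomes. Its adjusted mortality, quality-of-life and falls models include surgery type and falls history, but it sets out no delirium analysis. Nothing in the text supplied changes the primary analysis. Some protocol sentences are cut off in that text, so a secondary stratified or adjusted analysis in the lost parts cannot be excluded.

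**The concern.** Blocking within strata keeps the arms nearly equal in each stratum, so differences in risk between strata contribute almost nothing to the real sampling error of the risk difference. The crude standard error still counts them. If delirium risk differs between strata, the primary p value is on average slightly too large and the nominal 95% interval covers slightly more than 95%. What is at stake is a little precision on the primary endpoint, which the trial could recover from data it already holds.

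**Working it through.** **Inputs from the protocol.** Sample Size Calculations i): 616 per arm, two-sided 5% level, and control risk as in "we conservatively assume an incidence of postoperative delirium in the routine anesthesia care group of 25" percent. The falls-history share is taken as 33% from Sample Size Calculations iii): "Based on a study that showed a preoperative fall prevalence of 33% over six months preoperatively in a similar patient population".

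**Assumptions, not in the documents.** Cardiac share 20% to 50%; the two factors independent; risk gaps written as cardiac + falls history, in percentage points; a constant 7-point drop.

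**The plan's own figures.** The normal approximation with 616 per arm and 25% control risk gives power of 84.9%, 93.2% and 97.5% for drops of 7, 8 and 9 points. The stated bounds (above 80%, 90% and 95%) hold. The crude half-width at 25% against 18% is 1.96 × √[(0.25×0.75 + 0.18×0.82)/616] = 4.57 points, an interval of 2.4 to 11.6. The protocol gives roughly 3 to 12 and names no interval method.

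**Formulas.** Let c be the cardiac share, g and h the cardiac and falls gaps, and B the between-stratum variance.

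- B = g²·c(1−c) + h²·0.33·0.67
- r = 1 − B/(0.25×0.75)
- True size of the plain test = 2[1 − Φ(1.96/√r)]
- Stratified half-width = 1.96·√[(0.1875 + 0.1476 − 2B)/616]
- True SE of the difference = √[(0.3351 − 2B)/616]
- Power = Φ[(0.07 − 1.96·SE₀)/true SE], where SE₀ = √[2×0.215×0.785/616] for the plain test and √[2(0.215×0.785 − B)/616] for the stratified test

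**Example, 20+10 at 50% cardiac.** B = 0.04×0.25 + 0.01×0.2211 = 0.01221; r = 0.935; size 4.27%; half-width 4.40; power 85.9% plain, 87.5% stratified.

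| Gaps | r | True size, plain test | Half-width, plain → stratified | Power gain |
|---|---|---|---|---|
| none | 1 | 5.0% | 4.57 → 4.57 | 0 |
| 5+5 | 0.994–0.995 | 4.93–4.94% | 4.57 → 4.56 | 0.1–0.2 points |
| 10+10 | 0.975–0.980 | 4.71–4.77% | 4.57 → 4.51–4.52 | 0.5–0.6 |
| 20+10 | 0.935–0.954 | 4.27–4.48% | 4.57 → 4.40–4.45 | 1.2–1.6 |

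Ranges run over cardiac shares of 20% to 50%. With an effect proportional to risk instead of constant, the gains are 0.1 to 1.2 points.

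**Simulation.** 200,000 trials per setting, 1,232 patients, random stratum sizes, blocks of 20 with incomplete last blocks, 35% cardiac, 33% falls history. Each pair is the plain test, then Cochran-Mantel-Haenszel (CMH).

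- No spread: null rejection 5.00% and 4.99%; power 85.2% and 85.1%.
- 10+10: null rejection 4.70% and 4.97%; power 85.3% and 85.9%; coverage 95.2% and 94.9%.
- 20+10: null rejection 4.34% and 5.03%; power 86.0% and 87.5%; coverage 95.8% and 95.1%.

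At a 7-point drop, the two tests disagree at 0.05 in about 0.6% (10+10) to 1.6% (20+10) of trials with complete data, and in about 1.3% to 2.4% with 10% of outcomes missing at random. Most disagreements favour the stratified test, but not all: with 10% missing, the plain test alone is significant in about 0.3% of trials.

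**The case against.** The strongest reply is that nothing here is an error. A prespecified crude chi-square and risk difference are valid and slightly conservative, the stated power is met without stratifying, and the declared purpose of the strata is balance, which the design delivers. All of that stands, so the point is an improvement and not a fault in validity.

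Support for prognostic strata is also mixed. Statistical Analyses i) calls both factors known risk factors. The Background's list of consistently described risk factors names neither, and the longer list under Delirium Prediction Models does not name them explicitly; falls could enter there only through frailty indices. The 20+10 setting at 35% cardiac implies control risks from 14.7% to 44.7%, a spread that no figure in the documents supports. That is why the range starts at no effect.

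The protocol also limits how much hangs on the 0.05 line: a p value just under it "should be considered as preliminary, and future studies should be conducted for corroboration", and Strengths and Limitations expects follow-up studies even after a non-significant decrease.

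A reader might infer that the significance verdict can change only when the plain p value lies just above 0.05. That would hold only if the crude and stratified estimates were identical. Incomplete blocks and missing outcomes make them differ: about 27–45% of changed verdicts fall outside such a window (upper end about 0.053 for 10+10 and 0.057 for 20+10) with complete data, and 58–71% with 10% missing, in both directions.

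**Conclusion.** The point holds as a minor matter of efficiency and calibration, confined to the primary delirium test and its interval. Under the assumed gaps, true size is about 4.9% to 4.3% in place of 5%, the reported half-width is about 0.01 to 0.17 points too large (4.57 against 4.56 to 4.40), and 0.1 to 1.6 points of power are forgone at a 7-point drop. If the strata carry no prognostic information, nothing material is lost.

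A reader might infer that ignoring the strata biases the estimate, inflates type I error or leaves the trial underpowered. The documents support none of these: the departure is in the conservative direction, and all three stated power bounds are reproduced with the plain test.

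The direction is firm if the strata are prognostic. The size is not, because it depends on stratum risks and a cardiac share that the documents do not give.

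**What to change.** **If delirium data are still blinded:** make the primary analysis a CMH test with a Mantel-Haenszel stratified risk difference and 95% interval over the four randomisation strata, and keep the plain chi-square as a sensitivity analysis.

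**If they are already unblinded:** leave the plain chi-square as the primary test and report the stratified result as a labelled supplementary analysis, so that the primary test is not changed after the results are known.

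The documents do not show which case applies. The SAP's matched-cohort section dates ENGAGES surgery from January 2015 to May 2018, so recruitment had probably ended or nearly ended when it was written.

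The cost is one sentence. The strata are already recorded, no patients are added, and the target remains a risk difference: in the 10+10 and 20+10 simulations, the two estimates correlate above 0.999 with complete data and at 0.996 with 10% missing. At a 20% cardiac share the smallest stratum would hold about 0.20 × 0.33 × 1,232 = 81 patients, enough for Mantel-Haenszel weights.
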